9.3 Pregnancy

If a woman becomes pregnant while on study treatment, study treatment must be discontinued. The investigator must counsel the subject and discuss the risks of continuing with the pregnancy and the possible effects on the fetus.

9.3.1 Reporting of pregnancy

Irrespective of the treatment received by the subject, any pregnancy occurring after study start (i.e., signing of informed consent) up to EOS must be reported within 24 hours of the investigator's knowledge of the event.

Pregnancies must be reported on the Idorsia Pregnancy form, which is faxed to Idorsia Global Drug Safety (see contact details provided on the Pregnancy form), and on an AE page in the eCRF.

9.3.2 Follow-up of pregnancy

Pregnancies must be followed-up to their conclusion for all randomized subjects and the outcome must be reported to Idorsia Global Drug Safety.

Any AE associated with the pregnancy occurring during the follow-up period after DB study treatment discontinuation must be reported on separate AE pages in the eCRF. Any SAE occurring during the pregnancy must be reported on an SAE form as described in Section [9.2.5](#).

9.4 Study safety monitoring

Study safety information (AEs, SAEs, laboratory values, ECGs, vital signs, and study-specific examinations as required) is monitored and reviewed on a continuous basis by the Idorsia Clinical Team (in charge of ensuring subjects' safety as well as data quality). In addition, an IDMC and an ISB are monitoring safety data [see Section [3.3](#)].

10 STATISTICAL METHODS

All statistical analyses will be conducted by Idorsia or by designated CROs supervised by Idorsia.

A Statistical Analysis Plan (SAP) will provide full details of the analyses, data displays, and algorithms to be used for data derivations.

10.1 Analysis sets

A subject must have given informed consent before being included in any analysis set.

10.1.1 Screened Analysis Set

The Screened Analysis Set includes all subjects who entered screening and have a subject identification number.

10.1.2 Full Analysis Set

The Full Analysis Set (FAS) includes all subjects assigned to a DB study treatment. In order to adhere to the intention-to-treat principle as much as possible:

- Subjects are evaluated according to the treatment and strata they have been assigned to, which may differ from the treatment they have received;
- All available data are included.

10.1.3 Per-Protocol Set

The Per-Protocol Set (PPS) comprises all subjects from the FAS who complied with the protocol sufficiently to be likely to exhibit the treatment effects. Criteria for sufficient compliance include exposure to treatment, availability of measurements, and absence of major protocol deviations that have an impact on the treatment effect. The full list of criteria will be finalized before unblinding treatment codes.

10.1.4 Safety Set

The Safety Set includes all subjects who received at least one dose of DB study treatment. Subjects will be evaluated according to the actual treatment they received, which may differ from the randomly assigned treatment.

10.1.5 Treatment Withdrawal Set

The Treatment Withdrawal Set comprises all subjects included in the Safety Set who received single-blind placebo treatment in the run-out period.

10.1.6 Pharmacokinetic Analysis Set

The Pharmacokinetic Analysis Set (PK Set) includes all subjects in the Safety Set who have at least 1 PK sample collected after initiation of DB study treatment. Subjects receiving placebo will be excluded from the PK set.

10.1.7 Patient Preferences Analysis Set

The Patient Preferences Analysis Set includes all subjects in the Safety Set who have answered at least one patient preferences questionnaire after initiation of study treatment.

10.1.8 Usage of the analysis sets

The analyses of efficacy endpoints including baseline and disease characteristics will be performed using the FAS, and the PPS for certain sensitivity analyses.

The Safety Set will be used for the analysis of safety endpoints (including previous and concomitant medications, and study treatment exposure).

Subject data will be listed using the Safety Set, unless otherwise specified.

The Treatment Withdrawal Set will be used for the analysis of endpoints used to assess withdrawal symptoms (e.g., BWSQ total score) and rebound insomnia (e.g., objective and subjective sleep parameters: WASO, LPS, TST, sWASO, sLSO, and sTST).

The analysis of ACT-541468 plasma concentrations 9–10 h post-dose will be performed using the PK Set.

The Patient Preferences Analysis Set will be used for the analysis of endpoints to assess patient preferences.

10.2 Variables

Detailed description of study efficacy and safety variables (endpoints) can be found in Section 6 of this protocol.

10.3 Description of statistical analyses

10.3.1 Analysis of the primary and secondary efficacy variables

10.3.1.1 Overall testing strategy

The Type I error rate will be controlled for the testing of multiple null hypotheses associated with the primary and secondary endpoints assessed at 1 and 3 months of treatment and the two dose levels included in this study, i.e., 25 mg and 50 mg.

The eight statistical null hypotheses associated with the primary efficacy endpoints are:

Sleep maintenance:

- $H1_{WASO}$: Higher Dose – Placebo = 0 for WASO at Month 1
- $H2_{WASO}$: Higher Dose – Placebo = 0 for WASO at Month 3
- $H3_{WASO}$: Lower Dose – Placebo = 0 for WASO at Month 1
- $H4_{WASO}$: Lower Dose – Placebo = 0 for WASO at Month 3

Sleep onset:

- $H1_{LPS}$: Higher Dose – Placebo = 0 for LPS at Month 1
- $H2_{LPS}$: Higher Dose – Placebo = 0 for LPS at Month 3
- $H3_{LPS}$: Lower Dose – Placebo = 0 for LPS at Month 1
- $H4_{LPS}$: Lower Dose – Placebo = 0 for LPS at Month 3

The eight statistical null hypotheses associated with the secondary efficacy endpoints are:

Sleep quantity:

- $H1_{sTST}$: Higher Dose – Placebo = 0 for sTST at Month 1
- $H2_{sTST}$: Higher Dose – Placebo = 0 for sTST at Month 3

- $H_{3_{sTST}}$: Lower Dose – Placebo = 0 for sTST at Month 1
- $H_{4_{sTST}}$: Lower Dose – Placebo = 0 for sTST at Month 3

Next day performance:

[figure not shown]
- $H_{1_{IDSIQ}}$: Higher Dose – Placebo = 0 for IDSIQ sleepiness domain score at Month 1
- $H_{2_{IDSIQ}}$: Higher Dose – Placebo = 0 for IDSIQ sleepiness domain score at Month 3
- $H_{3_{IDSIQ}}$: Lower Dose – Placebo = 0 for IDSIQ sleepiness domain score at Month 1
- $H_{4_{IDSIQ}}$: Lower Dose – Placebo = 0 for IDSIQ sleepiness domain score at Month 3

where ‘Higher Dose’, ‘Lower Dose’, and ‘Placebo’ represent the mean change from baseline for the given endpoint (WASO, LPS, sTST or IDSIQ sleepiness domain score) and time point (Month 1 or Month 3) for the 50 mg, 25 mg and placebo treatment group, respectively.

Each null hypothesis will be tested against the alternative hypothesis: that ACT-541468 improves WASO / LPS / sTST / IDSIQ sleepiness domain score at the given dose (25 or 50 mg) and time point (Month 1 or Month 3) compared to placebo.

The order of testing and the alpha level applied to each null hypothesis will be based on the Bonferroni-based gatekeeping procedure [Bretz 2009] (shown in Figure 2 below as a directed graph) that will control the study-wise Type I error at a two-sided 5% significance level. To account for the concurrent evaluation (multiple comparison) of two distinct endpoint categories (i.e., sleep maintenance and sleep onset) a Bonferroni correction is applied. Both endpoint categories will be tested at half of the two-sided 5% significance level. This supports the sponsor’s intention to make a superiority claim versus placebo for efficacy in either a sleep maintenance and/or sleep onset indication. The remaining hypotheses will be tested following the gatekeeping strategy moving from Month 1 to Month 3 for higher dose ACT-541468 vs placebo and then from Month 1 to Month 3 for lower dose ACT-541468 vs placebo. The pre-specified proportion of alpha that will be distributed once a given null hypothesis (node) is rejected is shown on the arrow in the directed graph. If a certain null hypothesis cannot be rejected, then the alpha level used for that test is absorbed at that node and not distributed further.

Figure 2 Hypothesis testing strategy

10.3.1.2 Hypotheses and statistical model

The main analysis will be performed using the FAS.

A longitudinal data analysis method (i.e., linear mixed effects model) will be used for the analysis of change from baseline in WASO, LPS, sTST, and IDSIQ scores, separately. All available data, regardless of occurrence of intercurrent events (e.g., study treatment discontinuation, the use of prohibited medication), will be included in the model.

The analysis model will adjust for the baseline value of the relevant response variable (either WASO, LPS, sTST or IDSIQ sleepiness domain score), age group (< 65; ≥ 65 years), treatment (higher dose; lower dose; placebo), time point (Month 1; Month 3), and the interaction of treatment by time point, and baseline by time point.

To evaluate the efficacy hypotheses, appropriate contrasts will be used to test the treatment differences of interest (i.e., the difference in Least Squares mean change from baseline between higher dose ACT-541468 vs placebo and lower dose ACT-541468 vs placebo at Month 1 and Month 3). An unstructured covariance matrix will be used to model the correlation among repeated measurements. This approach relies on the missing at random (MAR) assumption.

A term for ‘center’ is not included in the statistical model due to the low numbers of subjects expected in many centers. Randomization was not stratified by center for the same reason.

10.3.1.3 Handling of missing data

For WASO and LPS values, if one of the two values is missing either for baseline, Month 1 or Month 3, the single value available will be used as the mean for this time point. Otherwise, the mean value will be considered missing for that time point.

For sTST values, subjects must have at least 3 days of data during each week to calculate a weekly mean. Otherwise, the mean value will be considered missing for that week.

For IDSIQ sleepiness domain scores, subjects must have at least 4 days of data during each week to calculate a weekly mean. Otherwise, the mean value will be considered missing for that week.

Note that the above implies implicit imputation: the missing data point(s) is(are) given the same value as the mean of the non-missing data point(s) of that same week or time point.

10.3.1.4 Supportive/sensitivity analyses

The impact of deviations from the MAR assumption underlying the linear mixed effects model as well as the incidence and pattern of missing values will be explored in order to evaluate the possible impact on results and will be described in the SAP.

The analysis performed for the primary and secondary endpoints will be repeated using the PPS in order to assess the effect protocol deviations have on the results.

10.3.2 Analysis of other efficacy variables

Summary statistics will be provided for other efficacy endpoints using either number (%) of subjects for categorical variables or descriptive statistics (e.g., mean, SD, median, min., max.) for continuous variables. Further details will be described in the SAP.

10.3.3 Analysis of the safety variables

Analyses of safety endpoints will be performed using the Safety Set, unless noted otherwise.

Adverse events

AEs will be coded using MedDRA. The number (%) of subjects experiencing a TEAE (including SAEs, AESIs after adjudication by the ISB, and AEs leading to premature discontinuation of the DB study treatment) will be summarized by System Organ Class (SOC) and/or PT, and maximum intensity. A subject with multiple intensities reported for an AE will be summarized under the maximum intensity recorded for the event. A subject with multiple occurrences of an AE is counted only once in the AE category (e.g., SOC, PT).

Laboratory data

Laboratory analyses will be based on data received from the central laboratory. Observed values and changes from baseline to Month 1 and Month 3 in both hematology and blood chemistry laboratory parameters will be summarized. The number (%) of subjects having a marked laboratory abnormality during DB study treatment will be tabulated.

Vital signs and weight

Observed values and changes from baseline to Month 1 and Month 3 in vital signs (mean of the two PSG nights in systolic and diastolic BP, and pulse rate) will be summarized.

Observed values and changes from baseline to Month 3 in body weight will be summarized.

Electrocardiograms

Observed values and changes from baseline to Month 3 for each ECG parameter (QTcB, QTcF, heart rate, PR, QRS) will be summarized. The number (%) of subjects having a marked ECG abnormality during DB study treatment will be tabulated.

Withdrawal symptoms

The Treatment Withdrawal Set will be used to assess the potential for withdrawal symptoms.

The BWSQ total score will be summarized using descriptive statistics for the observed values and changes from the last assessment on DB treatment (Visit 8, 2nd morning) to the beginning and the end of the treatment withdrawal period (in the morning at Visit 9 and at Visit 10, respectively).

In addition, withdrawal symptoms after DB study treatment withdrawal will be assessed through the incidence of AEs and marked ECG abnormalities occurring during the treatment withdrawal period. The number (%) of subjects having, separately, an AE and a marked ECG abnormality during the treatment withdrawal period will be tabulated.

Insomnia rebound effect

The Treatment Withdrawal Set will be used to assess the potential for rebound insomnia.

The changes from baseline to the treatment withdrawal period (Visit 9, run-out) in objective sleep parameters (WASO, LPS and TST) will be summarized using descriptive statistics.

The changes from baseline (mean value based on the screening sleep diary entries performed at home in the 7 days immediately preceding the first PSG at Visit 3) to the treatment withdrawal period (after PSG night at Visit 9) in subjective sleep parameters (sWASO, sLSO, and sTST) will be summarized using descriptive statistics.

Next-day residual effect

Observed values and changes from baseline to Month 1 and Month 3 in Coding sub-test[®], SDS[®], and VAS scores (mm) assessing morning sleepiness, daytime alertness and daytime ability to function, will be summarized.

C-SSRS[®]

Number (%) of subjects with suicidal ideation, suicidal behavior, and/or self-injurious behavior without suicidal intent based on the C-SSRS[®] during DB treatment will be tabulated.

Shifts from baseline showing any changes in suicidal ideation and suicidal behavior during DB treatment will also be provided. Subjects will be summarized under the worst of the following three categories, shown here in the order from best to worst: 1) No suicidal ideation or behavior, 2) Suicidal ideation only, and 3) Suicidal ideation and behavior.

10.3.4 Analysis of pharmacokinetic variables

PK analyses will be performed using the PK Set.

Descriptive statistics (n, mean, standard deviation, coefficient of variation [CV%], m [number of non-zero concentrations], geometric mean, geometric standard deviation, geometric CV%, median, minimum and maximum) of the ACT-541468 plasma

concentrations collected approximately 9–10 h post-dose (morning after the second PSG night) at Visit 6 and Visit 8 will be provided.

Exposure-safety analysis

The exposure-safety relationship will be explored using C_{9–10h} (plasma concentrations of ACT-541468 in the morning after the second PSG night at Visit 6 and Visit 8) and will be based on the PK Set. Safety parameters considered for this analysis will likely include selected AEs (e.g., somnolence), changes from baseline in Coding sub-test[®], SDS[®], VAS scores (mm) assessing morning sleepiness, daytime alertness and daytime ability to function, and other parameters as relevant. Further details will be described in the SAP.

10.3.5 Subgroup analyses

Subgroup analyses will be conducted to explore the uniformity of the overall treatment effects with regards to efficacy and safety variables, and will be described in the SAP.

10.3.6 Analysis of the patient preferences variable

Discrete choice data from the PAUSE sub-study will be analyzed using multinomial logit, random parameter logit, latent class and heteroscedastic conditional logit models. Socio-demographic and clinical characteristics, and health literacy and numeracy data will be collected from the study participants, and used as covariates for assessing preference and scale heterogeneity. The results of the DCE may be used to specify the weights and partial value functions in a quantitative benefit-risk assessment (BRA) of insomnia treatments. The BRA will be run both deterministically and probabilistically and will facilitate a stochastic multicriteria acceptability analysis (SMAA). The SMAA will involve running up to 10,000 iterations of the BRA, each time sampling weights and performance inputs from pre-specified distributions. Further details on analysis of the PAUSE sub-study will be provided in a separate SAP.

10.4 Interim analyses

No formal interim analysis will be performed for determining whether to stop (or modify) the study early (i.e., no hypothesis testing will be conducted *ad interim*). Therefore, no adjustment for multiple testing is required. This study includes an IDMC and ISB that will assess the safety of ACT-541468 on a regular basis as per the IDMC and ISB charters, respectively. To support the review of the safety and efficacy data by the IDMC, blinded data will be provided by Idorsia (or designated CRO) for the open sessions, and unblinded data will be provided by the ISAC for the closed sessions.

10.5 Sample size

[figure not shown]
The assumptions used to calculate sample size are provided in [Table 2](#).

Table 2 Sample size assumptions for primary and secondary endpoints

Endpoint at Month 1 & Month 3	Expected mean difference compared to placebo	SD per treatment group	Effect size (mean/SD)
WASO	15	40	≈ 0.37
LPS	15	40	≈ 0.37
sTST	20	54	≈ 0.37
[REDACTED]	█	█	█

IDSIQ = Insomnia Daytime Symptoms and Impacts Questionnaire; LPS = Latency to Persistent Sleep; SD = standard deviation; sTST = subjective Total Sleep Time; WASO = Wake After Sleep Onset.

[figure not shown]
The assumptions for the between-subject SD per treatment group are based on two recently completed Phase 2 studies (AC-078A201, AC-078A202) conducted in adult and elderly populations receiving 5 mg, 10 mg, 25 mg, 50 mg ACT-541468 and/or placebo. The minimal clinically relevant difference compared to placebo in the mean change from baseline to Month 1 and Month 3 in WASO, LPS, and sTST is 15, 15 and 20 min, respectively.

Based on a two-sample z-test, at least 900 subjects randomized to 50 mg ACT-541468, 25 mg ACT-541468, and placebo in a 1:1:1 ratio (i.e., 300 per group) provides 98.9% power to detect an effect size of 0.37 for a single hypothesis test. This accounts for the Bonferroni correction [Section 10.3], where the significance level (alpha) is halved and set to 2.5% two-sided. However, as the number of null hypotheses (endpoints) to test increases, the power decreases, as shown in the figure below [Figure 3]. The power calculation in the figure assumes all null hypotheses are independent (a conservative assumption for power calculations) and the curves for N = 250 per group and N = 350 per group are included for

reference. Consequently, 900 subjects will provide at least 90% power to detect an effect size of 0.37 for testing 9 independent null hypotheses.

Figure 3 Effect of testing multiple null hypotheses on power at a given sample size

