1.3 Purpose and rationale of the study

1.3.1 Purpose of the study

The main purpose of this Phase 3 study is to confirm that at least one dose of ACT-541468 is well tolerated and efficacious in promoting sleep onset and/or sleep maintenance in subjects with insomnia disorder.

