5.1.9 Premature discontinuation of study treatment

The decision to prematurely discontinue study treatment may be made by the subject, the investigator, or Idorsia personnel. The main reason for discontinuation must be documented in the eCRF and in the subject's medical charts (e.g., AE, lack of efficacy).

A subject has the right to prematurely discontinue study treatment at any time, without any justification, by withdrawal from study treatment only or by withdrawal from any further participation in the study (i.e., premature withdrawal from the study [see Section 8.2]). Although a subject is not obliged to give his/her reason for prematurely withdrawing from the treatment or the study, it is recommended that the investigator makes a reasonable effort to ascertain the reason(s), while fully respecting the subject's rights.

The investigator must discontinue study treatment for a given subject if, on balance, he/she believes that continued administration would be contrary to the best interests of the subject.

Study-specific criteria for discontinuation of study treatment are described in Section 5.1.10.

A subject who prematurely discontinues study treatment is NOT considered as withdrawn from the study and will be followed up until the planned EOS (Day 115), provided that the subject's consent for this limited participation in the study has not been withdrawn. The subject is recommended to return for safety assessments [see Table 1] within one week of his/her last DB study treatment intake (N.B., next day residual assessments will only be performed if the subjects can be assessed within 24 h of last DB study drug intake). All subjects withdrawn from study treatment are encouraged to follow planned study procedures (e.g., visits, sleep diary and questionnaire completion) until EOS. In this case, the run-out period (including Visit 9 and Visit 10) will not be performed, and subjects will directly enter the follow-up period after Visit 8 (considered as EOT in the event of premature discontinuation). The phone call will be performed as planned 30 days (+ 7 days) later, at Visit 11. This will decrease the amount of missing data which is important from a study integrity perspective. Subjects who prematurely discontinue study treatment or the study for any reason will not be replaced.

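### Does the 90% power statement for nine hypotheses in Protocol 10.5 misdescribe a plan that tests 8 primary and 16 total hypotheses, with no allowance for missing data?

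*Protocol*

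**What the plan says.** Protocol 10.5 bases the sample size on a two-sample z-test with 300 subjects per group. It gives 98.9% power for one test at an effect size of 0.37 and two-sided 2.5%. It notes that joint power falls as hypotheses are added, refers to Figure 3 for that relation (with further curves for 250 and 350 per group), and treats the hypotheses as independent, which it calls conservative. It concludes that "900 subjects will provide at least 90% power to detect an effect size of 0.37 for testing 9 independent null hypotheses".

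Table 2 is headed "Sample size assumptions for primary and secondary endpoints". It lists 15/40 for WASO and LPS and 20/54 for sTST, each rounded to about 0.37. The fourth row is redacted.

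Protocol 10.3.1.1 says that "The Type I error rate will be controlled for the testing of multiple null hypotheses associated with the primary and secondary endpoints". It lists eight primary hypotheses, then eight more ("The eight statistical null hypotheses associated with the secondary efficacy endpoints are"). On the primary split it says: "Both endpoint categories will be tested at half of the two-sided 5% significance level".

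On follow-up, Protocol 5.1.9 says both that "Subjects who prematurely discontinue study treatment or the study for any reason will not be replaced" and that "All subjects withdrawn from study treatment are encouraged to follow planned study procedures".

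**The concern.** Nine corresponds to nothing in the testing plan. The natural counts are 8 (primary), 12 (adding sTST) and 16 (adding IDSIQ). By the protocol's own method, nine is simply the largest number of tests that stays above 90% at 300 per arm. A reader who took the 90% to cover every alpha-controlled hypothesis would be misled, since joint power for 12 or 16 tests is lower.

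The calculation also uses every randomised subject. Section 10.5 names no missing-data rate and discontinued subjects are not replaced. SAP 6.1.4 expects intercurrent events to be somewhat more frequent than in Phase 2, and SAP 6.1.7 is largely devoted to missing data. At 0.37 the margin for the primary set is narrow. If the trial could not deliver its stated power for the primary hypotheses, the sample size would be in question.

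**Working it through.** **Inputs.** From Protocol 10.5: n = 300 per arm, two-sided alpha 2.5% (critical value 2.2414), effect size d = 0.37 (unrounded: 15/40 = 0.375 for WASO and LPS, 20/54 = 0.370 for sTST), independent tests. From Protocol 10.3.1.1: 8 primary and 8 secondary hypotheses.

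**Formula.** Power per test P = Φ(d·√(n/2) − 2.2414). Joint power for k independent tests = P^k.

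**Step 1: the protocol's own figures.** 0.37 × √150 = 4.5316, and 4.5316 − 2.2414 = 2.2902, so P = 0.98899. This matches the stated 98.9%. For nine tests, 0.98899^9 = 0.9052, which matches the statement of at least 90%. Ten tests would give 0.8952.

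**Step 2: the sets the plan does contain, full data.**

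| Set | k | d = 0.37 | Unrounded Table 2 |
|---|---|---|---|
| Primary (WASO, LPS) | 8 | 91.5% | 92.8% |
| Primary plus sTST | 12 | 87.6% | 88.8% |
| All, if IDSIQ is 0.37 | 16 | 83.8% | 84.9% |

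The 16-test row rests on two unknowns. With the others at 0.37, an assumed IDSIQ effect of 0.33 to 0.45 gives 75.6% to 87.4%. If the secondary nodes received 1.25% or 5% rather than 2.5% (the Figure 2 weights are not visible), 16 tests at 0.37 give 77.2% or 87.9%. The 12-test figure moves too: with unrounded effects and sTST tested at 5% it is 90.9%.

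**Step 3: missing data, primary set.** The documents give no rate, so 5% and 10% are assumptions; effective n is 285 and 270.

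| 8 primary hypotheses | Full data | 5% missing | 10% missing |
|---|---|---|---|
| d = 0.37, independent | 91.5% | 88.8% | 85.2% |
| d = 0.375, independent | 92.8% | 90.3% | 87.1% |
| d = 0.375, dose contrasts correlated 0.5 | 93.2% | 90.9% | 87.9% |

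The 0.5 in the last row follows from the shared placebo arm under 1:1:1 allocation and equal variances. For each endpoint and visit, the probability that both doses reject comes from the bivariate normal: 0.98248 at n = 300. Raising it to the fourth power, for two endpoints and two visits, gives 0.932.

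**Step 4: the margin.** At 0.37 under independence, 291 evaluable per arm (9 lost) gives 89.95% for the eight primary tests. At 0.375, 283 per arm (17 lost) gives 89.9%.

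**The case for a change.** The strongest case for a change is that section 10.5 itself chose joint power over several hypotheses as its justification, so it should name a set the plan tests. Table 2 claims to cover the secondary endpoints, yet the text gives no power for any set that contains them. With 2.5% at every node, the 12 tests with visible effects are already below 90% (88.8% even unrounded), so no IDSIQ value could lift 16 tests above that. A missing-data assumption is normal in a sample size section, and the sponsor holds the inputs, so the edit would be short.

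Part of this stands: the text neither explains nine nor states a missing-data rate. The rest is weaker. Joint power falls with k, so 90% for nine guarantees at least 90% for the eight primary hypotheses with full data. By its caption, Figure 3 plots power against the number of hypotheses and may well show 8, 12 and 16; its absence from the copy read here is not a gap in the plan. Its 250-per-group curve would also show the effect of 50 fewer subjects per arm (50/300 = 16.7%), although it is not labelled as a dropout allowance.

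On missing data, the only rate quoted, 3.9% in SAP 6.1.4, is Phase 2 treatment discontinuation. That is a different quantity. The plan keeps data collected after discontinuation, asks those subjects to continue visits, accepts one PSG night of two, and uses Month 1 data when Month 3 is missing. At 10% missing the primary set does fall below 90% on every row above, but neither document supports that rate.

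**Conclusion.** The sentence in Protocol 10.5 is correct as written and covers the primary family: 91.5% at 0.37, or 92.8% at Table 2's 15/40, with full data. At an assumed 5% missing, the primary figure is 88.8% on the most conservative inputs and 90.3% to 90.9% on Table 2's own effect size, so the stated power is not shown to be undelivered. Power for the 12 WASO, LPS and sTST hypotheses is about 87.6% at 0.37 and 2.5% per test. The figure for all 16 cannot be fixed from the public documents.

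The shortfall beyond the primary set does not weaken the design. The aim is to confirm that "at least one dose of ACT-541468 is well tolerated and efficacious in promoting sleep onset and/or sleep maintenance", which does not require rejecting all 16 hypotheses. Type I error control does not depend on the power statement.

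What remains is missing explanation: why nine, and what missing-data rate. A statistician can derive the power for any set from Table 2 and the stated method, given the redacted row and the graph weights. Writing it down would change no sample size, test or conclusion, so no change to the plan is needed.
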